The study participants will be recruited in two parallel cohorts – pregnant patients and non-pregnant patients. Pregnant patients tend to be healthy and without comorbidities, and the providers (anesthesiologists) that perform the neuraxial procedure tend to have significant experience. Non-pregnant patients tend to require neuraxial access for diagnostic or therapeutic purposes (i.e. not for the relief of labor pains), and therefore have comorbidities. Additionally, these providers (ER, neurology, etc.) tend to do far less of these procedures. Together, these two tracks provide the breadth of neuraxial access and therefore maximally determine early feasibility of this device.

For both pregnant and non-pregnant patients, the study procedure is the same. Eligible patients will be identified by chart review of various elements of the electronic medical record, as follows:

Labor & Delivery: Patients will be identified in communication with the OB anesthesia team that maintains an “electronic tracking board” in the interdisciplinary workroom in Prentice. Only patients early in labor, who are in relatively low amounts of pain and distress, will be approached by OB Anesthesia research nurses about the study. If the patient agrees to participate in the study she will be randomized that time to one of the three arms (palpation, US, or VerTouch).

Lumbar Puncture: Patients scheduled to undergo diagnostic or therapeutic lumbar puncture will be identified by appointment schedule and chart review. If a patient is determined to be eligible for the study by the provider responsible for the procedure the patient will be approached once availability of the study team is confirmed. The study team will arrange to be present for the procedure at the scheduled appointment time. The proceduralist or study team member will consent the patient, and if the patient agrees to participate in the study he/she will be randomized that time to one of the three arms (palpation, US, or VerTouch).

Randomization:

Prospective, randomized, controlled, observer blinded trial in patients undergoing neuraxial procedures for diagnostic, therapeutic, primary surgical anesthesia or labor pain management.

Group #1: VerTouch utilized for identification of site for labor epidural or spinal anesthesia procedure

Group #2: Ultrasound (US) utilized for identification of site for labor epidural or spinal anesthesia procedure

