All standard procedures for neuraxial procedures will be followed (standard practice) after site determination including time out, skin prep, hemodynamic monitoring, post-procedure instruction etc.

Zoomed in audio-less video of the procedure sight will be collected during at least 10 of the procedures, at each site, for inter-observer variability determination. If the subject has any identifying marks in or near the procedure site or refuses video capture of the procedure no video or images will not be collected in that subject. If the blinded observer is not present and the procedure cannot be recorded for any of the above reasons, the patient will be removed from the study.

Data collected on the VerTouch device will only be associated with the subject number when collected from device for technical evaluation of pressure sensor performance.

If US is used the provider chooses to save an image of the anatomy visualized the research nurse or staff will save that image under the subject number for post-hoc analysis of anatomy identified and image quality achieved.

DATA AND SPECIMEN BANKING

We will collect and data including reason for procedure, type of procedure, any anatomical issues affecting procedure (including but not limited to: scoliosis, positioning, BMI, paralysis), and age. The video/images collected will allow us to compare the observer variability.

SHARING RESULTS WITH PARTICIPANTS

Results will not be shared with participants.

STUDY TIMELINES

The individual will participate in the study for the duration of the procedure, which is usually approximately half an hour. It will take approximately one year to enroll all participants, and approximately 3 months to perform data analysis.

INCLUSION AND EXCLUSION CRITERIA

Inclusion criteria are any adult patients undergoing a neuraxial procedure. Necessary to this is the inclusion of pregnant women who make up a significant fraction of neuraxial procedures.

Exclusion criteria are those patients who do not speak English, have a plastic allergy, or are unable to consent.

Other special populations (individuals who are not yet adults, prisoners, vulnerable populations) will also be excluded.

If it is impossible to take a photograph that does not include identifying marks on the back (i.e. a birthmark or tattoo) the patient will be excluded from the video portion of the study

VULNERABLE POPULATIONS

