Patients can withdraw from the study at any time and their data will be deleted, and in no way will this impact their care since the study explicitly does not affect the standard of care. The study team will notify the PI by secure NM or NU email if a subject withdraws from the study.

RISKS TO PARTICIPANTS

No significant risk to the patient exists with the utilization of the VerTouch device. The materials on the device that come in contact with the patient are similar or the same as those that make up the US probes used in current state. The device is non-invasive and does not generate radiation or any other emission that would affect the patient's skin or underlying tissues.

POTENTIAL BENEFITS TO PARTICIPANTS

While there is no direct benefit to participants, we do hope that this will benefit pregnant and non-pregnant patients in the future who are undergoing neuraxial procedures. Our previous feasibility study did suggest that the use of the VerTouch may represent an improvement on the current gold standard of palpation.

DATA MANAGEMENT AND CONFIDENTIALITY

Based on the feasibility study data collected and published earlier this year at our institution the incidence of first insertion success when utilizing the VerTouch device is 90.1%. Using historical data from studies comparing Ultrasound to Palpation the first insertion success rates are 62.9 and 43.6%, respectively. When utilizing the anticipated incidence of first insertion success for the VerTouch device and Ultrasound to complete a sample size calculation, given Type 1 and Type 2 error are 0.05 and 80%, respectively, each group must contain 38 patients. Therefore, when including the control "palpation" group, the total population needs to be 114 patients. We plan to recruit 120 patients, 40 in each group, to ensure appropriate sample size and allow unknown possible exclusions of recruited patients."

All photographs will be maximally zoomed in. If it is impossible to take a video that does not include identifying marks on the back (i.e. a birthmark or tattoo) no image will be taken. Data will be stored in REDcap using NM password protected computers for data entry.

Data in REDcap is backed up nightly using NM servers which are only accessible to the NM IT administrator. Data in REDcap and pictures/videos will be destroyed 5 years after the completion of the study.

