Statistical analysis: Data will be compared between groups using the chi2 statistic or the Fisher's exact test. A $P < 0.05$ will be required to reject the null hypothesis.

PROVISIONS TO MONITOR THE DATA TO ENSURE THE SAFETY OF PARTICIPANTS
N/A (minimal risk study)

PROVISIONS TO PROTECT THE PRIVACY INTERESTS OF PARTICIPANTS

Patients in this study, whether undergoing neuraxial access for a disease-state or for the treatment of labor pains, will certainly be under some amount of stress. Having a needle placed into one's back, as is the case for neuraxial procedures, can be stress provoking. Extra care will be taken to approach them during a quiet moment when the clinical team has finished their evaluation. It will be emphasized that in no way will this impact their care, and in fact can help future patients undergo these procedures more quickly and safely to minimize their stress.

COMPENSATION FOR RESEARCH-RELATED INJURY
N/A

ECONOMIC BURDEN TO PARTICIPANTS

There is no cost to the patient to be in this study.

CONSENT PROCESS

Consent will take place in Prentice Women's Hospital 8th floor Labor and Delivery unit at a time mutually convenient to the clinical team, patient, and research team. Subjects will also be recruited from Galter, Lavin and Feinberg pavilions (numerous medical units). They will be offered to contemplate their participation up until 10 minutes prior to the time of their neuraxial procedure (if any less than 10 minutes were available for application of the VerTouch device prior to the clinical procedure, this would risk rushing the clinical procedure). REDcap electronic consent will be utilized to decrease the number of times the paper consent would be touched. Multiple

times throughout the process, the participant will be reminded that this in no way affects their standard of care and that participation can be withdrawn at any time.

NON-ENGLISH SPEAKING PARTICIPANTS

N/A

WAIVER OR ALTERATION OF CONSENT PROCESS

N/A

PROTECTED HEALTH INFORMATION (PHI AND HIPAA)

Does the study involve the creation, use, or disclosure of Protected Personal Health Information?

- Will a HIPAA Authorization be obtained from for all participants? Yes
-
- Name
- Age (years)
- Date of procedure
- Telephone numbers
- Medical Record Numbers
- Email address

QUALIFICATIONS TO CONDUCT RESEARCH AND RESOURCES AVAILABLE

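### BMI and procedure type are recorded and the cohorts are said to differ, yet the only planned comparison is unadjusted, which forgoes a modest, low-cost gain in precision

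*Combined protocol and SAP*

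**What the plan says.** All references are to the combined protocol and SAP.

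- **Data collected** (Data and Specimen Banking): reason for and type of procedure, and "any anatomical issues affecting procedure (including but not limited to: scoliosis, positioning, BMI, paralysis), and age". The label of affecting the procedure attaches to the anatomical items, BMI among them. Age and type of procedure are simply listed.
- **Cohorts** (Procedures Involved): pregnant patients are described as generally healthy and treated by experienced anesthesiologists. Non-pregnant patients are described as having comorbidities, with operators who do these procedures much less often. Participant Population(s) plans 60 of each.
- **Groups** (Randomization): Groups 1 to 3 mix two kinds of procedure, for example "VerTouch utilized for identification of site for labor epidural or spinal anesthesia procedure". Groups 4 to 6 are lumbar punctures. Allocation is by a computer-generated schedule; stratification is not stated in words.
- **Primary endpoint** (Study Endpoints): the total number of needle insertions and redirections, which is a count.
- **Size** (Data Management and Confidentiality): "given Type 1 and Type 2 error are 0.05 and 80%, respectively, each group must contain 38 patients", and then "We plan to recruit 120 patients, 40 in each group".
- **Analysis** (Statistical analysis paragraph, same section): "Data will be compared between groups using the chi2 statistic" or Fisher's exact test, at P < 0.05. No covariate, stratified test or regression model is named anywhere.

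**The concern.** The protocol identifies sources of variation in how hard a procedure is, records them, and then makes no use of them. With 40 patients per modality, or 20 per modality within a cohort, two things follow. Variation due to BMI, cohort and procedure type stays in the error term. And if one arm happens to receive heavier patients, or more epidurals than spinals, nothing planned corrects for it.

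Adjustment for a short, prespecified list of prognostic baseline variables usually improves power and does not bias a randomised comparison. If the list is not fixed in advance, an adjustment made after the data are seen would be open to the charge of selection.

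**Working it through.** **1. The plan's own figure.** Inputs from Data Management and Confidentiality: VerTouch first-insertion success 90.1%; for ultrasound and palpation, "the first insertion success rates are 62.9 and 43.6%, respectively"; alpha 0.05; the 80% given as type 2 error is read as power. Sidedness is not stated; two-sided is assumed.

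n = [z₀.₉₇₅√(2p̄(1−p̄)) + z₀.₈₀√(p₁(1−p₁)+p₂(1−p₂))]² / (p₁−p₂)², with p̄ = (0.901+0.629)/2 = 0.765.

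n = [1.960×0.5996 + 0.842×0.5679]² / 0.272² = 2.733/0.0740 = 36.9, so 37 per group. The plan's 38 is reproduced to within one patient. One-sided with continuity correction gives 36, so the match does not settle sidedness.

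Unadjusted power at 40 per arm: VerTouch v ultrasound 83.1%; VerTouch v palpation 99.8%; ultrasound v palpation 40.7%.

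**2. Variance formula, first-insertion success.** If covariates explain a share R² of the variance, effective n = 40/(1−R²). The documents give no R², so a range is assumed.

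| Assumed R² | Effective n | VerTouch v ultrasound | Ultrasound v palpation |
|---|---|---|---|
| 0 | 40.0 | 83.1% | 40.7% |
| 0.05 | 42.1 | 85.0% | 42.5% |
| 0.10 | 44.4 | 86.9% | 44.5% |
| 0.20 | 50.0 | 90.6% | 48.9% |
| 0.30 | 57.1 | 94.0% | 54.4% |

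**3. Simulation, first-insertion success** (4000 runs, 40 v 40, 20 per cohort in each arm). Assumed log-odds effects are for cohort and for one continuous covariate per SD. The adjusted analysis is a linear model with robust standard errors. VerTouch v ultrasound:

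| Cohort, covariate | Chi-squared | Adjusted | Change (points) |
|---|---|---|---|
| 0, 0 | 84.5% | 82.3% | −2.2 |
| 1, 0 | 85.5% | 84.3% | −1.2 |
| 1, 0.5 | 85.7% | 85.9% | +0.2 |
| 1, 1 | 86.1% | 88.6% | +2.5 |
| 2, 1 | 86.3% | 90.3% | +4.0 |

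Ultrasound v palpation, which is not a VerTouch comparison, moved more: from 44.0% to 39.7% (−4.3) with no effects, and from 42.0% to 50.4% (+8.4) with the strongest. A test stratified by cohort alone changed VerTouch v ultrasound by 0 to +2 points.

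**4. Simulation, total count** (1500 runs, 40 v 40; count = 1 + overdispersed Poisson, gamma shape 2; arm ratio exp(−0.8) on passes beyond the first; rank regression adjusted for cohort and BMI). All inputs are assumed, since the plan gives no mean or SD for the count.

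| BMI effect per SD | Cohort effect | Unadjusted | Adjusted | Change (points) |
|---|---|---|---|---|
| 1.42-fold | 1.65-fold | 71.4% | 74.3% | +2.9 |
| 1.65-fold | 1.65-fold | 68.5% | 75.2% | +6.7 |
| none | none | 68.1% | 67.5% | −0.6 |

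A separate run of 4000 gave +2.9, +5.8 and −0.6. Type I error lay between about 4% and 6% throughout.

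**5. Chance imbalance.** The difference in a covariate's mean between two arms has SD √(2/n) in units of the covariate's SD. For n = 40 this is 0.224, so a gap above 0.3 SD (0.3/0.224 = 1.34) occurs in about 18% of trials. For n = 20 it is 0.316 (0.3/0.316 = 0.95), or about 34%.

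**6. How many covariates.** At the planned rates, expected first-insertion failures are 40×0.099 = 4.0 with VerTouch and 40×0.371 = 14.8 with ultrasound. Only a short list can be supported. Under the group definitions and the two recruitment routes, lumbar puncture coincides with the non-pregnant cohort. Intercept, cohort and two procedure-type indicators make 4 columns of rank 3, so cohort and three-level procedure type cannot both be entered.

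**The case against.** The strongest reply is that nothing is invalid. Under randomisation the unadjusted test keeps its type I error, an unadjusted primary analysis is an accepted choice, and three arms within each cohort with 60 patients per cohort suggest that cohort will be roughly balanced anyway. All of that stands.

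The prognostic strength of BMI or cohort is also not in the documents, so every gain above rests on assumed effects and could be nil. That stands too, and it limits the point to a modest one.

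A third reply is that the larger defect is a chi-squared or Fisher test applied to a count. This is fair. In one set of runs, chi-squared on one pass versus more had 51% to 59% power where the adjusted count analysis had 74% to 75%, and most of that difference came from using the count. But repairing that mismatch already means writing a new model, and that is the natural moment to fix its covariates.

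Finally, the wording on BMI could mean that it is noted only when judged a problem, and no time of recording is given. A complete baseline BMI therefore cannot be taken for granted. This changes the fix but does not remove the point.

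**Conclusion.** The point holds as a recommended improvement in efficiency. The protocol gives its own reasons to expect BMI and cohort to matter, and then plans only an unadjusted test.

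The size is a range under assumptions: about 3 to 7 points of power on a rank analysis of the count; about −2 to +4 points for VerTouch versus ultrasound on first-insertion success in simulation (up to about +11, 83.1% to 94.0%, if R² were as high as 0.30); and nil for VerTouch versus palpation, already at 99.8%.

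A reader might infer more, and the documents do not support it:

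- **That the planned test is biased or invalid.** It is not; chance imbalance affects precision and the credibility of one result, not the error rate.
- **That the omission leaves the trial underpowered.** On the plan's own inputs, 40 per arm gives 83.1% for VerTouch versus ultrasound without adjustment.
- **That a definite amount of power is being lost at no cost.** No prognostic strength is given, and adjustment costs a little if there is none.
- **That age and type of procedure are called factors affecting the procedure.** Only the anatomical items, including BMI, carry that label; the case for procedure type rests on the description of the cohorts.

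**What to change.** Replace the sentence on the between-group test with a prespecified model for the total count: a proportional-odds or rank-based regression on arm, one three-level procedure factor (labor epidural, spinal, lumbar puncture) and continuous BMI. The procedure factor already carries cohort, so cohort should not also be entered.

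Specify in addition that:

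- BMI is recorded for every patient before allocation, and the procedure factor is the procedure planned at that time;
- positioning, and any other item judged after allocation, is left out;
- the covariate list is fixed before unblinding;
- the unadjusted comparison is reported as a sensitivity analysis.

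The simulations above used rank regression with cohort and BMI; a proportional-odds model with the three-level factor should be checked in the same way before it is adopted. A negative binomial model of the total count is not an obvious alternative. The count starts at 1, and in one simulation (1000 runs, assumed log-mean 0.3 for passes beyond the first) the fit gave no usable p-value in 15% to 42% of runs, a result that partly depends on software.

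The cost is SAP wording, a line on the data form to make BMI complete, and slightly more analysis work. If the covariates are not prognostic, expect to lose about 1 to 2 points of power on the count or on VerTouch versus ultrasound; the simulated loss for ultrasound versus palpation was about 4.

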PROTOCOL TITLE: Does the VerTouch Device Improve Insertion Site Identification for Lumbar Neuraxial Procedures when Compared to Palpation or Ultrasound Guided Site Selection? A Prospective Randomized Controlled Trial

PRINCIPAL INVESTIGATOR:

[name].
Department of Anesthesiology
[contact]
[contact]

VERSION DATE: 1.1 03/26/2021

STUDY SUMMARY:

Investigational Agent(s) (Drugs or Devices)	Intuitap VerTouch Device
IND / IDE / HDE #	
Indicate Special Population(s)	Children Children who are wards of the state Adults Unable to Consent Cognitively Impaired Adults Neonates of Uncertain Viability  Pregnant Women Prisoners (or other detained/paroled individuals) Students/Employees
Sample Size	120
Funding Source	Intuitap Medical
Indicate the type of consent to be obtained	 Written Verbal/Waiver of Documentation of Informed Consent Waiver of HIPAA Authorization Waiver/Alteration of Consent Process
Site	Lead Site (For A Multiple Site Research Study) Data Coordinating Center (DCC)
Research Related Radiation Exposure	Yes  No
DSMB / DMC / IDMC	Yes  No

OBJECTIVES:

Is there an identifiable difference in the number of insertions and redirections of the needle for a lumbar neuraxial procedure when the VerTouch device is used, instead of palpation (current gold standard) or ultrasound guidance (US), for the identification of the procedural insertion site?

Null Hypothesis:

There is no difference in the number of insertions and redirections of the needle for a lumbar neuraxial procedure when the VerTouch device is used.

BACKGROUND:

Literature:

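### The protocol recruits two cohorts that it describes as different, but neither the randomisation list nor the test is stratified by cohort: a cheap efficiency gain, not an error

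*Combined protocol and SAP*

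**What the plan says.** **Cohorts.** PROCEDURES INVOLVED opens: "The study participants will be recruited in two parallel cohorts", pregnant and non-pregnant. It describes the pregnant patients as generally healthy and treated by experienced anesthesiologists. The others have comorbidities, and of their operators it says "these providers (ER, neurology, etc.) tend to do far less of these procedures". VULNERABLE POPULATIONS adds that anatomy differs markedly in pregnancy. The accrual table in PARTICIPANT POPULATION(S) gives 60 pregnant women and 60 adults.

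**Arms and groups.** In the Labor & Delivery pathway, "she will be randomized that time to one of the three arms (palpation, US, or VerTouch"); the lumbar puncture pathway says the same. The Randomization subsection then numbers six groups by procedure type. Groups 1 to 3 begin with "Group #1: VerTouch utilized for identification of site for labor epidural or spinal anesthesia procedure", and groups 4 to 6 are the same modalities for lumbar puncture.

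**List.** Allocation is by a computer-generated schedule. No stratum, block or separate list is stated.

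**Size.** DATA MANAGEMENT AND CONFIDENTIALITY derives 38 per group from first-insertion success of 90.1% (VerTouch) and 62.9% (ultrasound), concludes that "the total population needs to be 114 patients" and goes on: "We plan to recruit 120 patients, 40 in each group".

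**Test.** The Statistical analysis paragraph compares groups by chi-square or Fisher's exact test at P < 0.05, with no cohort term.

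**The concern.** When a protocol recruits by cohort, numbers its groups by procedure and gives reasons to expect different success rates, the cohort is a natural stratification factor. Here it appears in neither the list nor the test.

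Two things are at stake, both modest. First, variation between cohorts stays in the error term of the pooled test, which costs power if the cohorts differ. Second, if the list does turn out balanced by cohort, the unstratified test uses a variance that is too large and falls below its nominal 5% level.

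A practical obstacle is that the stratum has no single definition. One section splits by pregnancy, the numbered groups split by procedure, and the accrual table contrasts pregnant women with adults.

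**Working it through.** **Inputs from the protocol:** success 90.1% and 62.9%; alpha 0.05 (taken as two-sided); power 80% (printed as the Type 2 error); 40 per arm; 60 per cohort. **Assumed:** the cohort gaps in success, because the documents give none.

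**1. The plan's own figure.** Pooled-variance formula, no continuity correction:

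n = [1.960·√(2·p̄·q̄) + 0.842·√(p₁q₁ + p₂q₂)]² / (p₁ − p₂)²

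with p̄ = (0.901 + 0.629)/2 = 0.765 and q̄ = 0.235. The first term is 1.960·√0.3596 = 1.175 and the second 0.842·√0.3226 = 0.478, so n = 1.653²/0.272² = 36.9, that is 37 against the stated 38. The sizing reproduces. Exact power at 40 per arm is 84.9% for chi-square and 78.5% for Fisher.

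**2. Three arms or six groups?** 3 × 38 = 114 and 3 × 40 = 120 match the stated totals; 6 × 38 = 228 and 6 × 40 = 240 do not. The sizing is for three modality arms with cohorts combined. With 60 per cohort, each modality has about 20 patients in each cohort under equal allocation.

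**3. Level of the unstratified test on a cohort-balanced list.** Take both arms at 62.9% overall, with an assumed gap g between cohorts. The pooled test uses variance 0.629 × 0.371 = 0.2334. With exactly 20 per cell, the true variance is that minus (g/2)².

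- g = 0.40: 0.2334 − 0.0400 = 0.1934. Ratio of standard deviations √(0.1934/0.2334) = 0.910. Effective critical value 1.960/0.910 = 2.153, so the true level is 3.1%.
- g = 0.20: 0.2334 − 0.0100 = 0.2234. Ratio 0.978, critical value 2.003, level 4.5%.

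Simulation over three null settings with a 40-point gap gives 2.7 to 3.1% with balanced cells and 4.8 to 5.2% when the list is not balanced by cohort. Uncorrected Cochran-Mantel-Haenszel (CMH) stays at 4.9 to 5.0%.

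**4. Power, VerTouch against ultrasound.** Simulation, 400,000 trials per scenario. The overall rates are held at 90.1% and 62.9%, and the ultrasound arm has the gap shown. Assumed cohort rates, VerTouch / ultrasound: 0.901, 0.901 / 0.629, 0.629; then 0.941, 0.861 / 0.729, 0.529; then 0.980, 0.822 / 0.829, 0.429.

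| Assumed gap | Allocation | Pooled chi-square | CMH, uncorrected | Change (points) |
|---|---|---|---|---|
| 0 | 20 per cell | 84.9% | 85.0% | +0.1 |
| 20 | 20 per cell | 85.4% | 86.0% | +0.6 |
| 40 | 20 per cell | 86.5% | 89.2% | +2.7 |
| 0 | simple, within cohort | 84.3% | 83.5% | −0.8 |
| 20 | simple, within cohort | 84.2% | 84.6% | +0.4 |
| 40 | simple, within cohort | 84.3% | 88.0% | +3.7 |

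Holding the modality odds ratio constant across cohorts instead gives a similar picture: at ultrasound gaps of 11, 23, 33 and 42 points the change is +0.2, +0.8, +1.7 and +2.7 with balanced cells, and −0.4, +0.5, +2.1 and +3.8 with simple randomisation.

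**5. Continuity correction.** With 20 per cell, CMH with the 0.5 correction has power 76.3%, 78.0% and 81.9% at gaps of 0, 20 and 40. The correction costs more than stratification gains.

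**6. If the endpoint is the count.** With an assumed geometric count and 20 per cell, Wilcoxon against van Elteren gives 87.6 vs 87.5%, 87.6 vs 88.6% and 89.5 vs 93.0% at the same gaps.

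**7. The stratum.** The Randomization subsection covers "neuraxial procedures for diagnostic, therapeutic, primary surgical anesthesia or labor pain management", and the inclusion criteria admit any adult having a neuraxial procedure. A non-pregnant patient having surgical spinal anesthesia is therefore in the non-pregnant cohort but in groups 1 to 3. Only two recruitment pathways are described, so few patients may be affected.

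**The case against.** The case for leaving the plan alone is substantial. The three-arm reading is already fixed: there is one null hypothesis ("There is no difference in the number of insertions and redirections of the needle" when the device is used) with no cohort in it, both pathways name three arms, and the totals are multiples of three. Procedure type cannot be randomised, so allocation to the numbered groups can only mean choosing a modality within procedure type. The pooled test holds its level or is conservative. The gain depends on assumed gaps and reaches 3 to 4 points only at a large one. Exactly 20 per cell is also optimistic, because patients who can be neither observed nor recorded are removed and withdrawn patients' data are deleted. All of this stands, and it keeps the point small. What it does not supply is a stated list structure, a single stratum definition or a reason to leave the cohort out of the test.

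Three stronger readings are tempting, and the documents do not support them.

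- A reader might infer that the trial is underpowered because each numbered group has about 20 patients (exact chi-square power 55.1% for VerTouch against ultrasound). No within-cohort test is planned, and the sizing is for pooled arms.
- A reader might infer that the test runs across all six numbered groups and could reject because of a cohort difference alone. No such test is proposed, and the null hypothesis concerns the device only.
- A reader might infer that omitting the cohort invalidates the pooled comparison. Step 3 shows that it does not.

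**Conclusion.** The point holds as a cheap improvement. The sample size reproduces, and the pooled three-arm comparison is valid. Stratifying list and analysis by one cohort variable is the better method in a trial that itself describes its cohorts as different. The change in power runs from about −0.8 points (no cohort difference, unbalanced cells) through about +0.5 (20-point gap) to about +3 to +4 (40-point gap). It also brings the level back from about 3% to 5% in the balanced-list, 40-point case.

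These figures rest on the protocol's overall success rates, 60 patients per cohort, a two-sided 5% test of VerTouch against ultrasound, and assumed cohort gaps. Confidence is high that stratification is not stated and that the stratum has more than one definition. How much is gained cannot be known from the documents. The undefined word groups in the sample-size and analysis paragraphs needs only a wording change.

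**What to change.** 1. Define the cohort stratum once, and reconcile the pregnancy split in PROCEDURES INVOLVED, the procedure split in groups 1 to 6 and the accrual table. The recruitment pathway (Labor & Delivery or lumbar puncture) is one candidate that is known before randomisation. State where a surgical-anesthesia patient belongs.
2. Generate the randomisation list separately within that stratum, about 20 per modality.
3. Stratify the primary comparison of the three pooled modality arms by the same variable: CMH without continuity correction if the endpoint is binary; a stratified rank test (van Elteren) or a model with a cohort term if it is the count. Rule out the continuity correction in the text.
4. As wording only, state that groups in the sample-size and Statistical analysis paragraphs means the three modality arms with both cohorts combined.

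The list and the test should change together, since balancing the list alone makes the unstratified test conservative. The cost is some wording, one agreed definition and separate lists by stratum if these are not already intended. No patients are added, and at worst about 0.8 points of power are lost. This does not settle whether the primary endpoint is binary or a count, or how the three arms are tested against each other; those need their own decisions.
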